8.2 Analysis Methods

(1) Analyses related to safety evaluation

In the safety analysis set, the primary analysis items will be the occurrence of common ADRs and the incidence of ADRs (proportion of patients with AEs with which Celsentri's causal

relationship could not be denied). In addition, when tabulating the incidence of ADRs by factor such as patient background characteristics, factors affecting the onset of ADRs will be also examined.

(2) Analyses related to efficacy evaluation

Efficacy parameters for anti-HIV drugs such as a CD4 count, number of HIV-RNA copies and CDC classification will be tabulated and analyzed by patient background characteristic to examine factors affecting the efficacy of Celsentri. In patients tested for tropism, the relationship with the status of tropism change will be also evaluated.

9. Organization System for the Implementation of the Survey

The survey will be conducted using the system described in Appendix 3 in accordance with the procedures for the implementation of the HRD cooperative investigation (Appendix 2). The procedures for notifying ADRs, etc. are presented in Appendix 4.

This survey will be performed as a cooperative investigation by companies marketing drugs for the treatment of HIV infection^{Note 1)} using a common CRF. The common CRF for the drug use-results survey may be completed one copy for one patient even if a few anti-HIV infection drugs are coadministered during the reexamination period.

10. Name and Address of the Contractee, and the Scope of the Concerned Outsourced Activities

(1) Contractee

Address: PPD [redacted]

Name: PPD [redacted], PPD [redacted] CMIC PMS Co., Ltd.

Name of the person responsible for implementation: PPD [redacted], Postmarketing Surveillance Operation Implementation Supervisor

(2) Scope of outsource activities

- 1) Request to and contract with institutions
- 2) Issuance of a user's ID and password to each investigator
- 3) Retention of the originals of enrollment forms
- 4) Sending the copies of enrollment forms
- 5) Verification of registration and investigation items entered and sent by the investigators
- 6) Collection of the originals of CRFs
- 7) Preparation and collection of the statement of confirmation
- 8) Sending the copies of CRFs
- 9) Arranging reinvestigation items
- 10) Request for a reinvestigation
- 11) Retention of the originals of CRFs
- 12) Sending the CRFs (final version)
- 13) Data locking
- 14) Coding
- 15) Data tabulation/analyses

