Type of concomitantly-used anti-HIV drugs	Count the breakdowns of designated concomitantly-used anti-HIV drugs. Of note, when a patient used multiple drugs in the same classification, count the drugs as one. <Multiple-answers are acceptable in this column> [Stratification] Nucleoside reverse transcriptase inhibitor, non-nucleoside reverse transcriptase inhibitor, protease inhibitor and integrase inhibitor
Presence/absence of a concomitant CYP3A inducer	Presence/absence of designated CYP3A inducers that are concomitantly used (See the sheet “A list of CYP3A inducers”). [Stratification] Concomitant CYP3A inducer “present”, Concomitant CYP3A inducer “absent”
Haemophilia	“Present” should be selected when the codes applicable to haemophilia are included in the complication classification “1. haemophilia” or “8. Others” provided in the CRF at the first administration of CELSENTRI Tablets. [Stratification] Absence, Presence, Unknown/not provided
Classification of haemophilia	Classify it into “present” for the presence/absence of haemophilia. Classify non-A or non-B as “others”. For the classification, give priority to the value provided in the CRF at the first administration of CELSENTRI Tablets. [Stratification] A, B, Others
CDC classification of seriousness prior to administration	It should be within 30 days prior to the first administration of CELSENTRI Tablets and the closest date to the first administration date should be displayed (the administration date is also included). Of note, if you cannot enter the value because no such value is available within 30 days before the first administration of CELSENTRI Tablets, the applicable value should be entered only when the value obtained prior to the first administration is the same as the one after the administration was started (The number of days does not matter. Note that the value should be provided in the survey form of the contract year). [Stratification] A, B, C, Unknown/not provided, P-0, P-1, P-2, Unknown/not provided

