*A list of adverse reactions per patient background, etc.	Prepare a list for adverse reactions in <General Definitions>. © Displayed items: No., patient registration number, age, pediatrics, the elderly, race, presence/absence of pregnancy, presence/absence of complications, haemophilia, renal disorder, hepatitis A, hepatitis B, hepatitis C, others, liver disorder, syphilis, others, presence/absence of haemophilia, presence/absence of liver disorder, presence/absence of renal disorder, name of complication, presence/absence of allergy, presence/absence of concomitant treatment, name of concomitant treatment, presence/absence of concomitant drugs, number of concomitant drugs, presence/absence of concomitant anti-HIV drugs, number of concomitant anti-HIV drugs, administration period, long-term administration, presence/absence of adverse events, presence/absence of adverse reactions, name of adverse reactions (PT), seriousness, outcome, days to the onset, relationship with CELSENTRI
Incidence of adverse reactions per patient background	Prepare a table of incidence of adverse reactions on the following patient-background items: Follow the above <<Handling of Items>> for the definitions of each item per background. © Displayed items: primary disease, sex, presence/absence of pregnancy, age, inpatient/outpatient classification, treatment history of HIV infection, race, route of transmission, duration of disease, medical history, allergy, complication, type of complication, renal disorder, liver disorder, the mean daily dose, administration period, administration period [cumulative], total dose, total dose [cumulative], continued/discontinued, concomitant drug, number of concomitant drugs, type of concomitant drugs, number of concomitant anti-HIV drugs, type of concomitant anti-HIV drugs, presence/absence of CYP3A inducer, presence/absence of haemophilia, haemophilia AB, CDC classification of severity prior to administration, tropism classification at the first administration, concomitant treatment, blood coagulation factor (all cases and the cases with haemophilia) Calculate the minimum and the maximum for age, duration of disease, the mean daily dose, administration period, total dose while calculate the

	mean and the standard deviation for age as well (Of note, as to the description age for example, calculate the age of a patient in his 30s will be calculated as 30 years old).

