In the list of *, use a row for an adverse reaction; enter multiple adverse reactions in the equivalent number of rows for a patient. Entry of a patient number, etc. should be repeated.

4) Table for “Patients in the efficacy analysis group”

A table and a chart of changes in HIV-RNA load/CD4	
Prepare a chart and table on the changes in HIV-RNA load/CD4 in patients with and without treatment history, with and without concomitant CYP3A inhibitors, sex, with and without complications, with and without concomitant drugs, CDC classification and for all patients in the efficacy analysis group.
 
Pre-administration (Month 0) should be the most recent date within 30 days before administration including the first administration date.
 
For post-administration (Month 3, 6, 9, etc.), choose the value obtained on the most recent date within ±45 days from each point of Month 3, 6, 9, etc. If a “test value” is missing either before or after administrations, it should not be included in the chart.
 
Use a line chart with test values on the y-axis and months after administration (for every 3 months) on the x-axis.
 
For each point, extend the whisker in a single direction to show the SD value.
 
When you have n=1 for each point, display it with a dot without connecting it with a line.
 
Of note, for the maximum number of HIV-RNA copies detected, replace it with 399 from the initiation of survey to March, 2008, with 39 from April, 2008 to 2010 and with 19 in and after 2011 (depends on the site). Handle the encoded values, etc. as follows: Replace the values with inequality sign with the following [1] to [3] in calculation:

--	--

	
[1] <400: The value that you subtract 1 from the figure without inequality sign. Note that the inequality sign must be removed from the figures with inequality sign. For example: change "<20" to "19", "<40" to "39", "≤20" to "20", "≤40" to "40"
 
[2] ≥400 and <100000: Missing
 
[3] ≥100000: the value without inequality sign. For integer values less than 400 with no inequality sign, use them as they are without replacement.

Patients included in the chart [data in each plot]	Display the patient registration numbers and test results for each point of Month 0, 3, 6, 9, etc. to the number of HIV-RNA copies and CD4, the output data in the above graph.

5) Changes in tropism

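### When no CDC class falls in the 30-day pre-dose window, the SAP assigns baseline class only if it matches a class recorded after treatment started, so a baseline stratum depends on an on-treatment value

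*SAP*

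**What the plan says.** The rule is in the SAP under Handling of items, at the entry for CDC class before administration.

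- **Primary rule.** "It should be within 30 days prior to the first administration of CELSENTRI Tablets and the closest date to the first administration date should be" shown. The first administration date counts as inside the window. No later value is involved.
- **Trigger for the fallback.** It applies "if you cannot enter the value because no such value is available within 30 days before the first administration of CELSENTRI Tablets".
- **Fallback condition.** "the applicable value should be entered only when the value obtained prior to the first administration is the same as the one after" treatment began.
- **Time limits.** "The number of days does not matter. Note that the value should be provided in the survey form of the contract year".

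Apart from the class labels, the only category offered is unknown/not provided. The Test entry in the SAP's General Definitions leaves unknown and not-provided values out of testing.

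The variable is used in several places:

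- In SAP part 3, the adverse reaction incidence table by patient background lists "CDC classification of severity prior to administration, tropism classification at the first administration" among its factors. The list of adverse reactions and infections by background also includes baseline CDC class.
- In SAP part 4, the HIV-RNA and CD4 tables and charts are broken down by several factors, ending "with and without concomitant drugs, CDC classification and for all patients in the efficacy analysis group". This entry does not say that the class meant is the pre-administration one.
- Protocol 8.2(2) treats the same variable as an outcome: "Efficacy parameters for anti-HIV drugs such as a CD4 count, number of HIV-RNA copies and CDC classification will be tabulated and analyzed".

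**The concern.** A baseline factor should be fixed by what was known up to first dose. Here, for patients without an in-window value, membership of a baseline stratum depends on a later value of the same variable, and the protocol counts that variable as an efficacy parameter. Two patients with the same pre-dose record can be classified differently only because of what was recorded after treatment started.

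The protocol's objectives include factors that affect safety and efficacy (Section 1). Section 7.10(i) asks for infections and malignancies to be stratified by background characteristics as a priority item on immune competence. CDC class is an obvious factor for both. If the strata are partly selected on later course, comparisons between them are harder to interpret.

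The fallback need not be rare. The survey admits retrospective patients (Protocol 3) and patients already on treatment at contract (Protocol 5.2), and forms are completed yearly (Protocol 5.4). The documents do not say how often it will be used.

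**Working it through.** The documents state no figure on this point, so there is none to reproduce. The check has three parts.

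**1. Trace of the rule**

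| Class in 30-day window | Older pre-dose class | Post-start class | Baseline class assigned |
|---|---|---|---|
| B | any | C | B |
| none | B | B | B |
| none | B | C | unknown/not provided |
| none | B | A | unknown/not provided |
| none | B | none recorded | unknown/not provided |

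The first and third rows show the inconsistency: the same later course leaves one patient in the stratum and removes the other.

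**2. Comparison with the SAP's other baseline rules**

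The general definition of prior to administration, and the Month 0 rule for HIV-RNA and CD4 in part 4, both use dates up to and including first administration only. Neither requires agreement with a later value. Nothing elsewhere in the SAP lifts the condition for CDC class or provides a sensitivity analysis for it.

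**3. Illustration on assumed inputs**

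Let f be the share of a stratum with no in-window value and p the share whose class changes. Neither is in the documents. Assume that p is the same with and without an in-window value, that every fallback patient has an eligible older class and a post-start class, and that every change is caught by the comparison.

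Share of the stratum moved to unknown = fp.

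Share of changers among those left = (1 − f)p / (1 − fp).

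| p | f = 0.2 | f = 0.5 | f = 0.8 |
|---|---|---|---|
| 10% | 0.08/0.98 = 8.2% | 0.05/0.95 = 5.3% | 0.02/0.92 = 2.2% |
| 20% | 0.16/0.96 = 16.7% | 0.10/0.90 = 11.1% | 0.04/0.84 = 4.8% |

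For adverse reaction incidence, let r0 apply to patients whose class does not change and r1 to those whose class does.

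Full stratum: T = p·r1 + (1 − p)·r0.

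After removal: (T − fp·r1) / (1 − fp).

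Difference: −fp(1 − p)(r1 − r0) / (1 − fp).

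With r0 = 20% (assumed):

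- r1 = 20%: no difference, whatever f and p.
- f = 0.3, p = 10%, r1 = 40%: T = 22.0%. After removal, (0.22 − 0.03 × 0.4)/0.97 = 0.208/0.97 = 21.4%, which is 0.6 points lower.
- f = 0.5, p = 20%, r1 = 60%: T = 28.0%. After removal, (0.28 − 0.10 × 0.6)/0.90 = 0.22/0.90 = 24.4%, which is 3.6 points lower.

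The sign follows r1 − r0, on which the documents are silent.

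**The case against.** The strongest defence is that the condition is a validity check. When the older value may be of any age, an equal later value brackets the first dose and supports the class carried across it. A patient recorded as A some months before treatment and C afterwards may already have been C at first dose, and keeping that patient in A would be an error. The requirement that the value be in the contract-year form plausibly bounds its age, since forms cover results to the end of March each year.

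Part of this stands. Some mismatches will reflect change before first dose, and any rule that carries an older class forward will misclassify those patients. But the check also erases a known pre-dose class when the change came clearly after first dose, and when there is no post-start record at all. The contract-year limit does not remove the dependence on the post-start value.

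Several limits on reach also stand:

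- Patients with an in-window class keep it, whatever happens later.
- Those affected appear in a displayed unknown/not provided category. They remain in the safety and efficacy sets, the overall counts and the all-patient charts.
- The test exclusion is a general rule for all unknowns, and the tables concerned name no test for CDC class.
- The SAP does not say which post-start value is compared. If it is the first or nearest, patients who change later stay in their stratum, and the table above is an upper bound on removal.

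A reader might infer that patients who progress on treatment generally drop out of their stratum, or that classes A and B are made to look safer and more responsive while C is untouched. The documents do not support this. The rule acts only in the fallback and on change in either direction. A missing post-start value affects C as much as A or B, and no link between change of class and adverse reactions, HIV-RNA or CD4 is given.

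**Conclusion.** The point holds for the fallback rule. Where no CDC class exists in the 30 days up to first administration, baseline class depends on a post-treatment value of a variable that the protocol names as an efficacy parameter. Patients whose class changed are selectively moved out of the CDC strata. This reaches the adverse reaction incidence table, the adverse reaction and infection list and, if the same variable is used there, the HIV-RNA and CD4 breakdown by CDC class. Overall adverse reaction incidence is not affected.

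Neither the size nor the direction of any bias can be computed from the documents. On the assumed inputs, the loss from a stratum (fp) runs from 2% (f = 0.2, p = 10%) to 16% (f = 0.8, p = 20%). The three adverse reaction examples give an understatement of 0 to 3.6 points, with the top figure needing r1 at three times r0. These are illustrations, not estimates. The change should be made because the flaw is one of principle and cheap to remove, not because a large distortion has been shown.

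**What to change.** **Baseline rule.** Define baseline CDC class from pre-dose data only. If there is no value within 30 days, use the last class recorded before first administration, whatever was recorded later, and flag it as older than 30 days. Either keep the contract-year form limit or state that it is dropped. Reserve unknown for patients with no eligible pre-dose class.

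**Reporting.** State how many patients are classified by the fallback and how many are unknown. Repeat the CDC-stratified tables using in-window values only, as a sensitivity analysis. That restriction selects on having a recent pre-dose record, not on later course. In SAP part 4, say which CDC variable is meant.

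**Cost.** One sentence in the SAP, one flag and a rerun of existing tables. Protocol 7.7 already collects test dates and CDC class, so no new data are needed. The downside is that an older value may put a patient in the wrong stratum if the class changed between that record and first dose. The flag and the sensitivity analysis show how much this matters.

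**Separate addition.** Protocol 8.2(2) promises tabulation and analysis of CDC classification as an efficacy parameter, but the SAP lists change tables only for HIV-RNA, CD4 and tropism. Add a table of baseline by post-dose CDC class for the efficacy group, naming the post-dose value used. This gap exists whatever is decided about the fallback.

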5.2 Patient Enrollment

(1) For patients who have been on drugs subject to the HRD cooperative investigation at the time of the contract or will start to receive them during the survey period, the investigator/subinvestigator should enter required information (medical record number or identification number, patient's initials [as necessary], gender, birth date [as necessary, age; e.g., age group], pregnancy status, inpatient/outpatient status, name of the drug surveyed and start date of treatment) on the enrollment screen of the EDC system, and send it using the user's ID and password issued for each investigator/subinvestigator. The patients' enrollment numbers will be issued by the EDC system. The sites that cannot connect to the external network should send or collect the data after inputting them in the SPC.

Patients who have been continuously on the drugs subject to the HRD cooperative investigation will be automatically continued to be enrolled based on data of the previous CRFs.

(2) The CRO should, as necessary, report the status of patient enrollment to the applicable companies using an HRD cooperative investigation control chart.

(3) Sites having a markedly high number of patients should first understand an expected number of new patients and then enroll new patients in the order of the re-enrollment of new patients on the day of enrollment in the HRD cooperative investigation among continuing patients and patient verification by the sites. The ratio of the number of re-enrolled continuing patients and newly enrolled patients should be adjusted. Overall, approximately 40 patients per investigator should be enrolled.

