Age	Calculate the Western-style age as of the initial administration date of CELSENTRI Tablets based on the date of birth. Of note, if the description only includes the year for date of birth in a site, describe it as "January 1". If it only includes the year and the month, replace it with "the first date of the month". If a "period of age" or "age" is provided in the "date of birth" column, select the "period of age" or "age" provided in the CRF when the patient was started on CELSENTRI Tablets only after confirmation that it is the data for the applicable year. [Stratification] [1] ≤14 years old, ≥15 and ≤64 years old, ≥65 years old, unknown/not provided [2] ≤9 years old, ≥10 and ≤19 years old, ≥20 and ≤29 years old, ≥30 and ≤39 years old, ≥40 and ≤49 years old, ≥50 and ≤59 years old, ≥60 and ≤69 years old, ≥70 years old, unknown/not provided
Inpatient/outpatient classification	Use the value in the CRF at the first administration of CELSENTRI Tablets. [Stratification] inpatient, outpatient, inpatient
Treatment history for HIV infection	Use the value in the CRF at the first administration of CELSENTRI Tablets. However, if an anti-HIV drug is administered prior to the initiation of CELSENTRI Tablets, select "2=present". [Stratification] Absence, Presence, Unknown/not provided
Race	Use the value in the CRF at the first administration of CELSENTRI Tablets. [Stratification] Japanese, others, unknown/not provided
Route of infection	Use the value in the CRF at the first administration of CELSENTRI Tablets. <Multiple-answers are acceptable in this column> [Stratification] Blood product, Mother-to-child transmission, Medical accident, Sexual transmission, Others, Unknown/not provided
Duration of disease	Calculate the years from infection to the first administration date. Display the minimum and the maximum as well. [Stratification] ≤1 year, >1 year and ≤2 years, >2 years and ≤3 years, >3 years and ≤4 years, ≥5 years, unknown/not provided
Medical history	Use the value in the CRF at the first administration of CELSENTRI Tablets. If there is an event that both occurred and recovered before the first administration of CELSENTRI Tablets in the 'adverse event' column, regard it as "present". [Stratification] Absence, Presence, Unknown/not provided
Presence/absence of allergy	Use the presence/absence of allergy provided in the CRF at the first administration of CELSENTRI Tablets. [Stratification] Absence, Presence, Unknown/not provided

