Patient composition ratio	Display the number of patients and the patient composition ratio for the following patient background items. Follow the above <<Handling of Items>> for the definitions of each item per background. ◎ Displayed items: primary disease, sex, presence/absence of pregnancy, age, inpatient/outpatient classification, treatment history of HIV infection, race, route of transmission, duration of disease, medical history, allergy, complication, type of complication, renal disorder, liver disorder, the mean daily dose, administration period, administration period [cumulative], total dose, total dose [cumulative], continued/discontinued, concomitant drug, number of concomitant drugs, type of concomitant drugs, number of concomitant anti-HIV drugs, type of concomitant anti-HIV drugs, presence/absence of CYP3A inducer, presence/absence of haemophilia, haemophilia AB, CDC classification of severity prior to administration, tropism classification at the first administration, concomitant treatment, blood coagulation factor (all cases and the cases with haemophilia) Calculate the minimum and the maximum for age, duration of disease, the mean daily dose, administration period, total dose while calculate the mean and the standard deviation for age as well (Of note, as to the description age for example, calculate the age of a patient in his 30s will be calculated as 30 years old).
Line list (Basic patient-background data)	Retrieve the items provided in the mock-up from CELSENTRI-Tablets data base. Of note, display the calculated or edited values for the items with (calculate result) provided under the item name in the mock-up.
A list of the reasons why the tropism assay was not conducted	Pick up the patients who did not undergo the tropism assay and retrieve the reasons why the test was not conducted.
A list of the patient summary for the survey	Prepare the list based on the sheet “A list of the patient summary for the survey”. See “166272A1” and “166272B1” in the mock-up.

3) Table for “Patients in the safety analysis group”.

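### Ages recorded only as a decade are set to the decade's lowest year, which understates mean age, and the SAP does not say how such records enter the ≤14 / 15–64 / ≥65 strata

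*SAP*

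**What the plan says.** Decade-only ages are an expected kind of record. Protocol section 5.2 lists among the enrolment data "birth date [as necessary, age; e.g., age group". The Age entry under Handling of items in the SAP starts from date of birth, but where an age or age period stands in that column it says to "select the 'period of age' or 'age' provided in the CRF when the patient was started on CELSENTRI Tablets", once that is confirmed to belong to the right year.

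The conversion to a single year is stated elsewhere. Under Type of Tables, the Patient composition ratio entry asks for the minimum and maximum of several items, and continues: "while calculate the mean and the standard deviation for age as well". A parenthesis then gives the rule: "calculate the age of a patient in his 30s will be calculated as 30 years old". The entry on incidence of adverse reactions per patient background repeats both.

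The Age entry defines two stratifications. The first is "≤14 years old, ≥15 and ≤64 years old, ≥65 years old, unknown/not provided". The second uses ten-year bands, for example "≥30 and ≤39 years old, ≥40 and ≤49 years old". Both table entries refer back to Handling of items for the definition of each background item. The list of adverse events also shows calculated paediatric and elderly flags, without giving their cut-points.

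**The concern.** Replacing an interval by its lower end is a one-sided imputation. It can be right for a patient at the bottom of the decade and too low for everyone else, so the errors do not cancel as patients accumulate. The mean age reported in the background table and the adverse-reaction table is therefore too low whenever decade-only records exist. The minimum and maximum can be too low as well.

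A separate gap concerns the first stratification. Its cut-points, 14/15 and 64/65, fall inside the 10s and the 60s, so a record of either decade does not identify a stratum. Age is one of the factors by which adverse-reaction incidence is tabulated, and protocol section 8.2 asks for factors affecting the onset of adverse drug reactions to be examined. How these records are allocated should be written down and not left to the programmer.

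**Working it through.** The plan states no figure for this error, so there is nothing to reproduce. The check is direct arithmetic.

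**Inputs.** The lowest-year rule (SAP, Patient composition ratio, and the adverse-reaction incidence entry); the two stratifications (SAP, Age entry); Western-style age, read here as completed years. The distribution of ages within a decade and the share *f* of decade-only patients are not given and are treated as assumptions.

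**Step 1: error per decade-only patient.** Error = true age − lowest year of the decade.
- Completed years, uniform over 0 to 9: (0 + 1 + … + 9)/10 = 45/10 = 4.5 years.
- Continuous age, uniform over 0 to 10: 10/2 = 5.0 years.
- Weights falling linearly from 10 to 1 across the decade: 165/55 = 3.0 years.
- Weights rising linearly from 1 to 10: 330/55 = 6.0 years.
- Any single patient: 0 to 9 completed years.

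**Step 2: effect on the overall mean.** Understatement = *f* × 4.5 (completed years) to *f* × 5.0 (continuous).

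| *f* | Overall mean too low by (years) |
|---|---|
| 1% | 0.045–0.05 |
| 5% | 0.225–0.25 |
| 10% | 0.45–0.50 |
| 20% | 0.9–1.0 |
| 50% | 2.25–2.5 |

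**Step 3: the SD.** As an illustration only, assume true ages are normal with mean 45 and SD 11 and every record is a decade. In a simulation, the lowest-year rule moved the mean of completed-year age from 44.5 to 40.0 and the SD from 10.99 to 11.36. The main damage is to the mean.

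**Step 4: the strata, if the lowest year were carried over.** Each decade was compared with the cut-points.
- 10s → 10 → ≤14. Ages 15–19 would be misplaced.
- 60s → 60 → 15–64. Ages 65–69 would be misplaced.
- All other decades: every age falls in the same stratum as the lowest year.
- Ten-year bands: no age is misplaced.

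Under uniformity, five of the ten single years in each of these two decades are affected, so half of the decade-only records in each.

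**Step 5: the midpoint.** With lowest year + 4.5 (completed years), the expected error of the mean under uniformity is 4.5 − 4.5 = 0. Using 35 for the 30s would overshoot by 0.5 on that scale. A midpoint does not repair the first stratification: 14.5 and 64.5 lie between the bands, and rounding up to 15 and 65 would misplace ages 10–14 and 60–64 instead.

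**The case against.** A reader might infer that the SAP puts patients aged 65–69 into 15–64 and those aged 15–19 into ≤14, and that the paediatric and elderly flags are therefore wrong. The documents do not support that. The lowest-year rule appears only as a parenthesis to the summary statistics. The strata are governed by the Age entry, which selects the recorded period and converts nothing. The first stratification already has an unknown level, so the cautious allocation is open under the current text. The flags have no stated cut-point or derivation, and the SAP relies on mock-up sheets that are not part of the text. Even if the lowest year were carried over, only decade-only records would be affected, not all patients of those ages.

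It can also be said that mean age is only a background descriptor. No test, model or decision in the documents uses it. Decade-only recording is a fallback, and the number of such patients may be small.

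All of this stands, and it keeps the point minor. It does not remove it. The downward bias follows from a rule the SAP states, and the missing allocation rule remains missing: the only numeric conversion the SAP offers is the lowest-year one, so its reuse for the strata or flags is neither instructed nor excluded.

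**Conclusion.** The concern holds in two parts.

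First, following the SAP as written understates mean age for decade-only patients. The size is 4.5 completed years (5.0 in continuous age) if ages are uniform within the decade, and 3 to 6 completed years under linear tilts. The effect on the overall mean is proportional to the decade-only share and cannot be sized from the documents. At a share of 10% or less it is at most about half a year under uniformity.

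Second, the SAP leaves undefined how 10s and 60s records enter the three-band stratification and the calculated flags. Misclassification there is conditional on carrying over the lowest year. It is a risk created by a gap, not an error the plan prescribes. The ten-year bands are sound. This is an improvement worth making and does not threaten the survey's conclusions.

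**What to change.** 1. For mean and SD, replace the lowest year with the decade midpoint in completed years (34.5 for the 30s), in both table entries. State whether decade-only records count towards the minimum and maximum.
2. Report the number of patients whose age is known only as a decade, so that readers can judge the effect.
3. In the Age entry, state that decade-only 10s and 60s records go to the existing unknown level of the first stratification, unless the locked data already show the side of the cut-point. Apply the same rule to the paediatric and elderly flags and state their cut-points.
4. Leave the ten-year bands unchanged.

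The cost is a few sentences in the SAP and some simple reprogramming. The drawback is a few more patients in the unknown level, and these drop out of any test on that stratification because the SAP's Test entry excludes unknowns. The fix should not depend on fresh queries to sites, since the SAP records that the data were locked on March 26, 2018.
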